**Table 3-2: Dose Groups for Part B**

KM-819 Dose (mg)	Subjects on KM-819 (n)	Subjects on placebo (n)	Total Subjects in Group (n)	Age Group
30†	6	2	8	Young adult male subjects
100†	6	2	8	
200†	6	2	8	
400†	6	2	8	
200	6	2	8	Elderly male or post-menopausal female subjects

† Doses between the current planned range may be assigned depending on safety, tolerability, and pharmacokinetic data from previous subjects and cohorts.

All subjects will undergo a Screening period of up to 28 days and an 8-day Confinement period when they are hospitalized for study activities (Day -1 to Day 8). Subjects are required to return for a Follow-up Visit on Day 14. See Figure 3-2 for Part B MAD study design.

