5. RANDOMIZATION

In each dose cohort, 8 subjects will be randomized to have 6 subjects receiving KM-819 and 2 subjects receiving placebo in both Part A and Part B.

For further details of randomization scheme please refer the section 4.5.2 and 4.5.3 of the CSP.

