6.3.12.5 Steady State Assessment (Part B Only)

To evaluate whether steady state was achieved, statistical analysis of $C\tau$ levels will be performed before Day 7, after a log-e transformation of the data from all active treatment doses. Only pre-dose concentration on days 1-7 for the 7 day analysis will be included in the analysis. A mixed effect model

Kainos Medicine, Inc.

Final 1.0

KMCP-819-K101

14/Nov/2017

TP-EP.BS-WW-001-05

Effective date: 29 Jul 15

Related to: SOP-EP.BS-WW-002

Page 41 of 61

PAREXEL International

Statistical Analysis Plan

will be fitted separately with day as a continuous covariate and subject as a random effect. The coefficient of the slope of the day effect on the log-e scale for each treatment dose will be used to assess whether steady state was achieved on Day 7. Using the estimate of variance, the 90% confidence intervals for the slopes will be calculated. If the 90% limits for the slope is including one then steady-state is statistically confirmed.[Table 14.2.6].

An example of SAS code to assess achievement of steady-state is included here.

```
ODS output solutionf=stat;  
Proc Mixed;  
  by dose;  
  where (Day in (1,2,3,4,5,6,7));  
  class subject;  
  model logCtau = Day/cl alpha=0.1 solution;  
  random intercept/subject=subject type=un;  
run;
```

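### The steady-state rule in SAP 6.3.12.5 treats a 90% interval that contains one value as confirmation, with no margin, and prints that value on the wrong scale

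*SAP*

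**What the plan says.** SAP 6.3.12.5 analyses pre-dose concentrations in Part B: "Only pre-dose concentration on days 1-7 for the 7 day analysis will be included in the analysis". The model has day as a continuous covariate and a random subject intercept, and the example code runs it separately by dose: "model logCtau = Day/cl alpha=0.1 solution" and "random intercept/subject=subject type=un". The quantity judged is "The coefficient of the slope of the day effect on the log-e scale for each treatment dose". The decision rule is "If the 90% limits for the slope is including one then steady-state is statistically confirmed", with the result going to Table 14.2.6.

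On numbers per dose, SAP Section 5 says that "8 subjects will be randomized to have 6 subjects receiving KM-819 and 2 subjects receiving placebo in both Part A and Part B", and SAP 6.2.2 keeps placebo subjects out of the PK analysis set. That leaves 6 per cohort. The Part B dose tables list 200 mg for both a young and the elderly cohort, so a by-dose run could combine them into 12.

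Neither document gives an equivalence margin, a limit on interval width, an inconclusive outcome or a trough CV. Protocol Section 8.7 does not describe a steady-state test.

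**The concern.** There are two separate faults in one sentence.

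**Scale.** A slope on the log-e scale is 0 when troughs are flat. A slope of one means troughs multiply by e (2.72) each day. One is the no-change value only after exponentiation, which neither the text nor the code does.

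**Logic.** Steady state is a claim of absence of change. An interval that contains the no-change value shows only that a change was not detected. With no margin, a wide interval passes easily and a narrow one around a trivial slope fails. The verdict then depends on assay and subject noise as much as on whether the troughs are flat.

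What is at stake is interpretation. SAP Table 2 of Section 6.1.3 labels a Day 7 parameter as an average at steady state. The time-invariance comparison in SAP 6.3.12.4 (Day 7 AUC over a dosing interval against Day 1 AUC to infinity) is readable only if steady state holds. A formal confirmation in the study report would probably be cited alongside both.

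**Working it through.** The plan states no error rate or precision for this rule, so there is no figure of its own to reproduce.

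**Inputs**
- From the SAP: n = 6 active subjects, 90% CI, random intercept, day continuous.
- Usable days: 2 to 7. The Day 1 sample precedes any drug and has no logarithm if it is zero.
- From Protocol 5.3: predicted half-life 9.27 h.
- Assumed, because the documents give none: within-subject trough CV, 10% to 40%.

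**Standard error of the slope**
- sigma_w = sqrt(ln(1 + CV²)); SE = sigma_w / sqrt(n × Sxx).
- For Days 2–7, Sxx = 17.5, so n × Sxx = 105. Residual df = 36 − 7 = 29, t = 1.699.

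**1. The rule as printed.** At CV 40% the half-width is 1.699 × 0.0376 = 0.064. To include one, the estimated slope must lie between 0.936 and 1.064, which is a 2.5- to 2.9-fold rise every day. The probability is about 0 in every scenario tried, perfect steady state included.

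**2. Value corrected to 0; true rise of 25% over Days 2–7.** Slope = ln(1.25)/5 = 0.0446 per day. The probability that the interval includes 0 comes from the noncentral t with noncentrality slope/SE.

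| CV | sigma_w | SE | Slope/SE | Confirmed |
|---|---|---|---|---|
| 15% | 0.149 | 0.0146 | 3.06 | 9% |
| 20% | 0.198 | 0.0193 | 2.31 | 27% |
| 30% | 0.294 | 0.0286 | 1.56 | 55% |
| 40% | 0.385 | 0.0376 | 1.19 | 68% |

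With no drift at all the figure is 90% at every CV. With 12 subjects at 200 mg, the 25% rise is still confirmed 30% of the time at CV 30%.

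**3. Same estimate, different noise.** An observed drift of 2% per day has log slope 0.0198.
- CV 10%: 0.0198 ± 0.0165, ratio 1.003 to 1.037, not confirmed.
- CV 20%: 0.0198 ± 0.0328, ratio 0.987 to 1.054, confirmed.

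**4. The protocol's own half-life.** One-compartment troughs as a fraction of plateau on day d are 1 − 2^(−24(d−1)/9.27): 0.834, 0.972, 0.995, 0.999, then 1.000 on Days 6 and 7. The drug is at plateau from Day 4, but the low Day 2 value gives a fitted slope of 0.0285 per day, or exp(5 × 0.0285) = 1.15-fold over Days 2–7. The rule confirms about 16% of the time at CV 10%, 60% at CV 20%, 75% at CV 30% and 81% at CV 40%.

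**5. Long half-life.** At 43 h the Day 7 trough is 90% of plateau and the fitted slope is about 0.19 per day. The rule confirms 0.1% of the time or less at CV up to 40%. At 48 h (87.5% of plateau on Day 7) it confirms 0.0% at CV 30% and 0.5% at CV 50%.

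**6. A margin rule instead.** Require the 90% CI of the fold-change to lie within 0.80–1.25 (an illustrative margin; neither document gives one), n = 6, half-life 9.27 h.
- Days 2–7: passes about 16% at CV 20% and 2% at CV 30%, because of the Day 2 effect in step 4.
- Days 4–7: Sxx = 5, df = 24 − 7 = 17, t = 1.740, slope limit ln(1.25)/3 = 0.0744. At CV 20% the half-width is 1.740 × 0.0361 = 0.063 and it passes about 28%. At CV 30% the half-width is 1.740 × 0.0536 = 0.093, wider than the limit, and it passes about 1%.
- False confirmation when the true change sits at the margin is at most 5%.

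**The case against.** The strongest reply is that the harm is small. The drug-accumulation mechanism that would make a false confirmation matter, a long half-life, is detected almost always because the early troughs rise steeply (step 5). What remains is a slow log-linear drift, for which no mechanism is offered. At the only half-life in the documents, the likelier error is failing to confirm a drug that is at plateau. The verdict also gates nothing: AUC, CL/F and accumulation ratios are derived regardless, time invariance has its own ratio and CI, and trough values are listed and summarised. All of this stands, and it limits the point to a secondary PK assessment.

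It is also true that a margin rule would usually be inconclusive with 6 subjects, and that a model pooled over the young cohorts with one common slope could hide dose-dependent accumulation. Both stand as limits on the remedy.

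Three stronger readings are tempting and should not be drawn:
- That the text as printed passes drifting troughs. It would pass essentially nothing; the false-confirmation figures apply only after the scale is corrected.
- That the rule would miss slow build-up from a long half-life. With Day 2–7 troughs it would not.
- That high confirmation rates from a model restricted to the last few troughs describe this plan. The SAP text and code use Days 1–7.

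None of this defends the sentence itself. Correcting one to zero and stopping there leaves non-significance standing as proof.

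**Conclusion.** The decision sentence is wrong as written on two counts: the comparison value does not match the scale of the slope, and failure to exclude a value is called confirmation with no margin or precision requirement. After the scale is corrected, a true 25% rise over Days 2–7 is confirmed 9% to 68% of the time at CV 15% to 40%. A drug already at plateau from Day 4 is confirmed about 16% of the time at CV 10% but 81% at CV 40%. These figures rest on an assumed CV range, a random-intercept model with 6 complete subjects, and one-compartment troughs at the protocol's predicted half-life. They are a range, not an estimate for this drug. The false-confirmation risk concerns slow drift with noisy troughs. This should be changed, but it touches no primary safety conclusion.

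**What to change.** Delete the sentence that declares steady state confirmed. Back-transform the slope and report, per dose, the fold-change in trough over the analysed days with its 90% CI, naming those days and giving the no-change value on the matching scale (1 for the fold-change). State whether the young and elderly 200 mg cohorts are fitted separately.

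If the sponsor wants a formal verdict, pre-specify a margin and declare steady state only when the whole interval lies inside it; otherwise report inconclusive. Apply it to later troughs, for example Day 4 onward, because including Day 2 makes a drug already at plateau look as if it is rising. A model pooled over the young cohorts should be supportive only, shown beside the per-dose slopes.

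The cost is a few sentences and lines of code, with no new data. SAP changes are straightforward before database lock; after it, the SAP's own addendum route applies. The downside is candour about precision: with a 0.80–1.25 margin a cohort of 6 will usually be inconclusive (step 6). Reporting only the fold-change and CI avoids that and still removes the unsupported claim.

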6.3.13 Pharmacodynamic Variables

The analysis of the pharmacodynamic (PD) data will be based on the pharmacodynamic population.

In both Parts A and B, mean and absolute value change from baseline at each post-baseline measurements for:

- Bond and Lader Visual Analogue Scale (VAS) [Table 14.2.8.1 (Part A) and Table 14.2.8.2 (Part B)]
- Profile of Mood States (POMS) [Table 14.2.9.1 (Part A) and Table 14.2.9.2 (Part B)]
- Korean Wechsler Adult Intelligence Scale-IV (K-WAIS-IV) [Table 14.2.10.1 (Part A) and Table 14.2.10.2 (Part B)]
- C-SSRS

In Part B only, PD parameters in plasma and CSF including:

- alpha synuclein oligomer [Table 14.2.11]
- total Tau [Table 14.2.12]

PAREXEL International Statistical Analysis Plan

- phospho-Tau [Table 14.2.13]
- Ratio of CSF concentration/Plasma Cmax. [Table 14.2.14]

For Part A and Part B, the PD parameters (Bond and Lader Visual Analogue Scale (VAS) [Listing 16.2.9.4.1 (Part A) and Listing 16.2.9.4.2 (Part B)], Profile of Mood States (POMS) [Listing 16.2.9.5.1 (Part A) and Listing 16.2.9.5.2 (Part B)], Korean Wechsler Adult Intelligence Scale-IV (K-WAIS-IV) [Listing 16.2.9.6.1 (Part A) and Listing 16.2.9.6.2 (Part B)], C-SSRS [Listing 16.2.9.7.1 (Part A) and Listing 16.2.9.7.2 (Part B)],

In Part B only, PD parameters in plasma and CSF including: alpha synuclein oligomer [Listing 16.2.9.8], total Tau [Listing 16.2.9.9], phospho-Tau [Listing 16.2.9.10], Ratio of CSF concentration/Plasma Cmax. [Listing 16.2.9.11]) will be listed within each study part and by cohort and time point and will include both absolute values and changes from baseline. Listing of CSF Concentration of KM-819 will be presented [Listing 16.2.6.3 (Part B)].

The baseline for each of Bond and Lader Visual Analogue Scale (VAS), Profile of Mood States (POMS), Korean Wechsler Adult Intelligence Scale-IV (K-WAIS-IV), alpha synuclein oligomer, total Tau and phospho-Tau parameters will be the Day 1.

Pharmacodynamic data will be summarized using descriptive statistics (n, mean, SD, minimum, median and maximum).

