##### Single Dose and Day 1 of multiple doses

- $AUC_{last}$ : area under the plasma concentration-time from predose (time 0) to the last quantifiable concentration
- $AUC_{inf}$ : area under the plasma concentration-time curve from predose (time 0) extrapolated to infinity
- $AUC_{inf}(\%)_{extrap}$ : Percentage of  $AUC_{inf}$  that is due to extrapolation beyond  $t_{last}$
- $CL/F$ : apparent oral clearance
- $C_{max}$ : maximum plasma concentration determined directly from the concentration-time profile
- $\lambda_z$ : terminal elimination rate constant
- $t_{1/2}$ : apparent terminal elimination half-life
- $t_{lag}$ : lag time

- $t_{max}$ : time to achieve maximum observed plasma concentration determined directly from the concentration-time profile
- $V_z/F$ : volume of distribution
- Other parameters, as appropriate, including dose-adjusted parameters.

Day 7 of multiple doses

- $AUC_{tau}$ : area under the plasma concentration-time curve for a dosing interval
- $AUC_{last}$ : area under the plasma concentration-time from predose (time 0) to the last quantifiable concentration
- $CL/F$ : apparent oral clearance
- $C_{max}$ : maximum plasma concentration determined directly from the concentration-time profile
- $C_{min}$ : minimum plasma concentration determined directly from the concentration-time profile
- $C_{trough}$ : observed plasma concentration before dosing
- $R_{ac}(AUC)$ : observed accumulation by  $AUC$
- $R_{ac}(C_{max})$ : observed accumulation by  $C_{max}$
- $t_{lag}$ : lag time
- $t_{max}$ : time to achieve maximum observed plasma concentration determined directly from the concentration-time profile
- $V_z/F$ : volume of distribution
- Other parameters, as appropriate, including dose-adjusted parameters

Cerebrospinal fluid (CSF) PK parameter for KM-819 includes the following after multiple dose CSF sample collection:

- KM-819 concentration in CSF

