### ***3.2.3 Pharmacodynamic Endpoints***

In both Parts A and B, mean and absolute value change from baseline at each post-baseline measurements for:

- Bond and Lader Visual Analogue Scale (VAS)
- Profile of Mood States (POMS)
- Korean Wechsler Adult Intelligence Scale-IV (K-WAIS-IV)
- C-SSRS

In Part B only, PD parameters in plasma and CSF including:

- alpha synuclein oligomer
- total Tau
- phospho-Tau
- ratio of CSF concentration/Plasma  $C_{max}$

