6. Screening height and weight will be used for BMI calculation for assessment of eligibility.
7. Blood will be tested for HBsAg, anti-HAV IgM, anti-HCV Ab, and anti-HIV Ab.
8. All hematology and serum chemistry labs will be taken after fasting for a minimum of 8 hours.
9. Simple spine X-ray examination will only be conducted at Screening for healthy elderly cohort.
10. Plasma samples for pharmacokinetics of KM-819 will be obtained on Day 1 predose (within 30 minutes prior to study drug administration) and 0.25, 0.5, 1, 2, 4, 6, 8, and 12 hours postdose, predose on Days 2, 3, 4, 5, 6,

---

and on Day 7 predose (within 30 minutes prior to study drug administration) and 0.25, 0.5, 1, 2, 4, 6, 8, 12, and 24 hours postdose.

11. CSF samples for pharmacokinetic of KM-819 will be obtained on Day 1 (at -120 minutes to 0 minute prior to the first dosing) and on Day 7 (at 1 hour after last dosing).
12. CSF samples for pharmacodynamic of KM-819 will be obtained on Day 1 (at -120 minutes to 0 minute prior to the first dosing) and on Day 7 (at 1 hour after last dosing).
13. Plasma samples for pharmacodynamic of KM-819 will be obtained on Day 1 (within 30 minutes prior to study drug administration) and on Day 7 (at 1 hour after last dosing).
14. Bond and Lader VAS, POMS, and K-WAIS-IV will be performed on Day -1, on Day 1 and Day 7 at predose, 3, 6, 12, and 24 hours postdose ( $\pm$  30 minutes for each time point).
15. The version of the C-SSRS to be performed at Screening is the “Baseline-Screening for Phase 1,” and the version of the C-SSRS to be performed on Day 3 and Day 8 (or at ED) is the “Since Last Visit”.

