- vital signs measurement (predose)

- scales assessments (predose)
- PK blood sampling within 30 minutes before dosing

Study drug will be administered from 8:00 to 10:00.

The procedures to be performed at postdose are listed below:

- postdose PK blood sampling at 0.25, 0.5, 1, 2, 4, 6, 8, and 12 hours (see Table 7-2)
- Plasma PD sampling (at 1 hour postdose)
- CSF PK and PD sampling (at 1 hour postdose)
- postdose scales assessments at 3, 6, and 12 hours

The following assessments will be also performed during Day 7:

- concomitant medication
- assessment of AE

On Day 8, the procedures to be performed are listed below:

- concomitant medication
- assessment of AE
- vital signs measurement and physical examination
- ECG assessment
- hematology and biochemistry blood sampling
- urinalysis sampling
- PK blood sampling at 24 hour after last dosing
- scales assessments at 24 hours after last dosing
- C-SSRS assessment

Subjects will be allowed to leave the study center after completing all the procedures on Day 8.

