C_{max_D}	Maximum observed concentration divided by dose

*Parent drug only

This Table is applicable for Day7 of Multiple ascending dose (Part B).

All urine voided will be collected in the following intervals: pre-dose and 0-24 hours post-dose. Urine samples will be used for qualitative analysis of KM-819 and possible metabolic profiling, if appropriate, and will be reported separately. For cerebrospinal fluid (CSF) PK, the concentration of KM-819 will be listed and no other PK parameters will be calculated as there will be only one sample from each subject.

PAREXEL International
Statistical Analysis Plan

6.1.3.1 *Pharmacokinetic Parameter Calculation Methods*

PK parameters will be calculated by non-compartmental analysis methods from the concentration-time data using WinNonlin (WNL) Professional (Version 6.3 or higher) following these guidelines:

- Actual sampling times relative to dosing rather than nominal times will be used in the calculation of all derived PK parameters.
- There will be no imputation of missing data.
- Any subjects with more than one observed concentration data will be included in the PK analysis set provided that at least C_{max} and $AUC_{(0-t)}$ can be reliably calculated .
- If one or more non-quantifiable (NQ) values occur in a profile before the first measurable concentration, they will be assigned a value of zero concentration. If a single NQ value occurs between measurable concentrations in a profile, the NQ should generally be omitted (set to missing) in the derivation of pharmacokinetic parameters, statistical analysis, and the individual subject plots. If two or more NQ values occur in succession between measurable concentrations, the profile will be deemed to have terminated at the last measurable concentration prior to these NQs. For the purpose of individual subject plots, these NQs will be set to 0, and the subsequent measurable concentrations will be retained. For the derivation of pharmacokinetic parameters, these NQs and any subsequent measurable concentrations will be omitted (set to missing).
- PK parameters following single and repeat dose will be estimated according to the following guidelines:
 - C_{max} will be obtained directly from the concentration-time data.
 - t_{max} is the time at which C_{max} is observed.
 - λ_z will be estimated at terminal phase by linear regression after log-transformation of the concentrations:

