Table 14.2.2.2 Summary of Pharmacokinetic Parameters of KM-819 (Pharmacokinetic Population) (Part B)

Table 14.2.3.1 Statistical Analysis To Assess Dose Proportionality of KM-819 Pharmacokinetic Parameters (Power Model) (Pharmacokinetic Population) (Part A)

Table 14.2.3.2 Statistical Analysis To Assess Dose Proportionality of KM-819 Pharmacokinetic Parameters (Power Model) (Pharmacokinetic Population) (Part B)

Table 14.2.4 Statistical Analysis To Assess Dose Proportionality of KM-819 Pharmacokinetic Parameters (ANOVA Model) (Pharmacokinetic Population) (Part A)

Table 14.2.5 Statistical Analysis of Time Invariance of KM-819 Pharmacokinetic Parameters (ANOVA Model) (Pharmacokinetic Population) (Part B)

Table 14.2.6 Statistical Analysis To Steady State of KM-819 Pharmacokinetic Parameters (Pharmacokinetic Population) (Part B)

Pharmacodynamic Data

Table 14.2.8.1 Summary of Observed and Change From Baseline of Bond and Lader VAS (Pharmacodynamic Population) (Part A)

Table 14.2.8.2 Summary of Observed and Change From Baseline of Bond and Lader VAS (Pharmacodynamic Population) (Part B)

Table 14.2.9.1 Summary of Profile of Mood States (Pharmacodynamic Population) (Part A)

Table 14.2.9.2 Summary of Profile of Mood States (Pharmacodynamic Population) (Part B)

Table 14.2.10.1 Summary of Observed and Change From Baseline of Korean Wechsler Adult

PAREXEL International
Statistical Analysis Plan

Intelligence Scale-IV (Pharmacodynamic Population) (Part A)

Table 14.2.10.2 Summary of Observed and Change From Baseline of Korean Wechsler Adult Intelligence Scale-IV (Pharmacodynamic Population) (Part B)

Table 14.2.11 Summary of Observed and Change From Baseline of Alpha Synuclein Oligomer (Pharmacodynamic Population) (Part B)

Table 14.2.12 Summary of Observed and Change From Baseline of Alpha Total Tau (Pharmacodynamic Population) (Part B)

Table 14.2.13 Summary of Observed and Change From Baseline of Phospho-Tau (Pharmacodynamic Population) (Part B)

Table 14.2.14 Summary of Observed and Change From Baseline of Ratio of CSF Concentration/Plasma Cmax (Pharmacodynamic Population) (Part B)

Safety Data

Table 14.3.1.1.1 Summary of Treatment Emergent Adverse Events (Safety Population) (Part A)

Table 14.3.1.1.2 Summary of Treatment Emergent Adverse Events (Safety Population) (Part B)

Table 14.3.1.2.1 Summary of Treatment-Emergent Adverse Events by System Organ Class and Preferred Term (Safety Population) (Part A)

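### The CSF-to-plasma ratio sets a CSF sample fixed at 1 h against plasma Cmax at each subject's own tmax; report the simultaneous 1 h ratio beside it, with tmax, and drop its change from baseline

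*SAP*

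**What the plan says.** Protocol 3.2.3 lists the "ratio of CSF concentration/Plasma" Cmax among the Part B pharmacodynamic endpoints, and SAP 6.3.13 repeats it as "Ratio of CSF concentration/Plasma Cmax".

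- **CSF timing.** Protocol Table 7-2 schedules CSF before the first dose and "on Day 7 (at 1 hour after last dosing"). Section 7.2.3.1 agrees: "CSF PK and PD sampling (at 1 hour postdose"). There is therefore one on-drug CSF value per subject.
- **Denominator.** Protocol 3.2.2 defines Cmax as the "maximum plasma concentration determined directly from the concentration-time profile", so it falls wherever that subject peaks. Cmax is derived on both Day 1 and Day 7, and neither document says which day enters the ratio.
- **Plasma at 1 h.** Day 7 plasma sampling is scheduled "and on Day 7 predose (within 30 minutes prior to study drug administration) and 0.25, 0.5, 1, 2, 4, 6, 8, 12" and 24 h. Table 7-4 gives the 1 h sample a window of ±5 minutes.
- **Other CSF measures.** The KM-819 concentration in CSF is an endpoint in its own right. SAP 6.1.3 derives no further CSF PK parameter, "as there will be only one sample from each subject". No time-matched ratio is planned and no reason for choosing Cmax is given.
- **Reporting.** In SAP section 8, Table 14.2.14 is titled "Summary of Observed and Change From Baseline of Ratio of CSF" concentration to plasma Cmax. SAP 6.3.13 also asks for changes from baseline in the listing (16.2.9.11). Yet the sentence there that assigns a Day 1 baseline names the scales and the three biomarkers and omits the ratio.

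**The concern.** The planned ratio can be factored:

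CSF(1 h)/Cmax = [CSF(1 h)/plasma(1 h)] × [plasma(1 h)/Cmax].

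The second factor is a property of the plasma curve, driven mainly by absorption rate, and carries no information about entry into CSF. It cannot exceed 1, and it falls as tmax moves beyond 1 h. Two dose groups, or the young and elderly cohorts, could have the same CSF entry and still show different ratios because one absorbs more slowly.

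KM-819 is aimed at a CNS disease, and the CSF values come from lumbar punctures in healthy volunteers. A reader will take this ratio as the penetration result.

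Two further gaps need no PK assumption. The day of Cmax is not named. And the table and listing call for a change from baseline of a quantity that has no meaningful baseline.

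**Working it through.** **Plan's own figure.** The documents give no expected value for the ratio, so there is nothing to reproduce. The inputs are consistent with each other: with the predicted CL 2.93 L/h and V 39.2 L (protocol 5.3), k = 2.93/39.2 = 0.0747 /h and ln 2/k = 9.27 h, the stated half-life.

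**Model.** The protocol's own form is used: one compartment, first-order absorption and elimination, F = 0.35, seven daily doses. The Day 7 concentration at t hours after dosing is

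C(t) = [F·Dose·ka / (V(ka − k))] × Σ over j = 0…6 of [exp(−k(t+24j)) − exp(−ka(t+24j))].

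F and dose cancel in the ratios. Cmax is read on the Day 7 sampling grid (predose, 0.25, 0.5, 1, 2, 4, 6, 8, 12, 24 h).

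**Assumptions not in the documents.** Human tmax is varied from 0.58 to 4 h. The animal oral values in protocol 1.2.1.3 are 0.58, 0.83 and 3 h, so 4 h is an extension. For each tmax, ka solves ln(ka/k)/(ka − k) = single-dose tmax. CSF equilibration is taken first as instantaneous, then as a first-order lag with half-life 0.25, 1 or 3 h. True penetration is set to 1 for everyone.

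**Instant equilibration (200 mg, mg/L).** Here CSF(1 h) = plasma(1 h), so the planned ratio equals plasma(1 h)/Cmax.

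| tmax (h) | ka (/h) | plasma 1 h | observed Cmax | planned ratio |
|---|---|---|---|---|
| 0.58 | 8.17 | 2.006 | 2.052 | 0.98 |
| 0.83 | 5.18 | 2.007 | 2.007 | 1.00 |
| 1 | 4.07 | 1.994 | 1.994 | 1.00 |
| 2 | 1.61 | 1.710 | 1.859 | 0.92 |
| 3 | 0.91 | 1.380 | 1.693 | 0.82 |
| 4 | 0.59 | 1.144 | 1.627 | 0.70 |

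The simultaneous ratio is 1.00 in every row.

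**With a CSF lag.** Range over tmax 0.58 to 4 h, and largest value divided by smallest:

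| lag half-life | CSF(1 h)/Cmax | spread | CSF(1 h)/plasma(1 h) | spread |
|---|---|---|---|---|
| none | 0.70–1.00 | 1.4-fold | 1.00 | none |
| 0.25 h | 0.57–0.92 | 1.6-fold | 0.81–0.94 | 1.17-fold |
| 1 h | 0.41–0.56 | 1.4-fold | 0.50–0.58 | 1.14-fold |
| 3 h | 0.37–0.39 | almost none | 0.38–0.56 | 1.45-fold |

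Up to a lag half-life of about 1 h, the time-matched ratio is the steadier one. At 3 h the order reverses.

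**Day of Cmax.** In the same model, Day 7 Cmax divided by Day 1 Cmax is 1.20 to 1.23 over these tmax values. For tmax 1 h, the Day 1 Cmax is 70 × 4.073/(39.2 × 3.998) × (0.928 − 0.017) = 1.66, and 1.994/1.66 = 1.20. Two programmers choosing different days would report ratios about 20% apart.

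**Baseline.** The Day 1 CSF sample is drawn in the 120 minutes before the first dose. No drug has been given and no Cmax exists, so there is no baseline ratio to subtract. Pairing that sample with a later Cmax would give a value near zero by construction, and the change would simply restate the Day 7 ratio.

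**The case against.** The strongest reply is that the distortion depends on kinetics nobody yet knows. If CSF lags plasma by hours, Cmax is the better denominator and a 1 h ratio creates the very artefact complained of. The 3 h row bears this out. So a reader might infer that the 1 h ratio should replace the Cmax ratio, but the documents do not support that, because they give no equilibration rate.

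Three other inferences go too far.

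- **A large error.** One could push the ratio to 38% low, but only with ka = 0.3 /h (tmax about 5.4 h), well beyond the animal range. At 0.58 to 1 h the shortfall is at most 2%.
- **The only CNS-exposure measure.** It is not. CSF concentration is a separate endpoint, listed in 16.2.6.3 and summarized under protocol 8.7. The ratio is the only planned CSF-to-plasma measure.
- **Tablet count or age as the cause of different tmax.** Nothing in the documents links either to tmax, and tablet count does not rise steadily with dose: 30, 100, 200 and 400 mg are 3, 1, 2 and 4 tablets.

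It is also fair that the endpoint is descriptive, with six active subjects per cohort and no formal PD test (SAP 6.3.13.1). Concentrations are listed and tmax is reported, so a reader could derive the 1 h ratio by hand. That limits the harm, but it does not explain why the SAP should leave the derivation to the reader.

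**Conclusion.** The point holds conditionally. The mismatch in timing is certain from the documents; its effect is not. When CSF follows plasma within about an hour and tmax is later than 1 h, slower absorption is reported as lower penetration. With instant equilibration the ratio is 0–2% low at tmax 0.6–1 h, about 18% low at 3 h and about 30% low at 4 h. With a lag half-life near 3 h the Cmax ratio is nearly unaffected and the 1 h ratio is the more distorted one. These sizes rest on the protocol's predicted CL and V and on assumed tmax and CSF kinetics.

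The unnamed day of Cmax and the missing baseline are defects whatever the kinetics. No error rate or test is affected, only the interpretation of a descriptive comparison between cohorts. This is a cheap improvement, not a flaw that undermines the study.

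**What to change.** In SAP 6.3.13, Table 14.2.14 and Listing 16.2.9.11:

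1. Report two Day 7 ratios side by side: CSF(1 h)/plasma(1 h), with the actual sampling times of both listed, and CSF(1 h)/Day 7 Cmax, with the day written into the definition.
2. Show each subject's Day 7 tmax in the listing and the cohort summary of tmax in the table.
3. State that neither ratio on its own is to be read as CNS penetration. Agreement between the two, or divergence that follows tmax, is what helps interpretation.
4. Delete change from baseline for the ratio.

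No new sample is needed: protocol 6.1.1 already captures actual times for both blood and CSF. The cost is one derived variable, a revised title and a few lines of text. The limitation remains that a single on-drug CSF time point cannot separate lag from penetration, and the extra ratio does not change that.
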